7.2.3 Adverse Event Relationship to Investigational Product or Procedure

An Investigator listed on Form FDA 1572 may make the determination of relationship to the biopsy, REACT injection procedure or REACT investigational product for each AE. Definitions of relatedness categories are:

- **Not Related:** Exposure to the study treatment did not occur, or the occurrence of the AE is not reasonably related in time, or the AE is considered unlikely to be related to the study treatment.
- **Unlikely Related:** The study treatment and the AE were not closely related in time, and/or the AE could be explained more consistently by causes other than exposure to the study treatment product.
- **Possibly Related:** The study treatment and the AE were reasonably related in time, and the AE could be explained equally well by causes other than exposure to the study treatment product.
- **Related:** The study treatment and the AE were reasonably related in time, and the AE was more likely explained by exposure to the study product than by other causes, or the study treatment was the most likely cause of the AE.

For the purpose of safety analyses, all AEs judged by the Investigator to be “possibly related” or “related” will be considered treatment-related adverse events. If relationship to biopsy, REACT injection, or REACT product is missing, then the adverse event is assumed to be related for analysis purposes.

7.2.4 Serious Adverse Events

A serious adverse event (SAE) is an adverse event that occurs during any phase of the study (i.e., baseline, treatment, washout, or follow-up) at any dose of the investigational product, comparator, or placebo, and fulfills one or more of the following:

- Results in death
- It is immediately life-threatening
- It requires in-patient hospitalization or prolongation of existing hospitalization
- It results in persistent or significant disability or incapacity

- Results in a congenital abnormality or birth defect
- It is an important medical event that may jeopardize the subject or may require medical intervention to prevent one of the outcomes listed above.

All SAEs that occur from the day of the biopsy procedure, during treatment, or within 24 months following the final REACT injection, whether or not they are related to study procedures or the investigational product, must be recorded in the subject's medical record as well as the CRF provided by the Sponsor or its designee.

7.2.5 Adverse Event Summaries

All AEs (serious and non-serious) will be classified by SOC and PT using MedDRA.

For AEs, the following will be summarized and presented for the IAS. Note that summaries of treatment-emergent AEs only apply to the IAS as all subjects in the IAS have been treated. Summaries of AEs during the pre-injection period apply to both the IAS (treated) and FAS (biopsied). Firstly, the overall summary of AEs and summaries for the pre-injection period will be presented for the IAS. If there are more subjects in the FAS (biopsied) than the IAS (treated), then the overall summary of AEs and the pre-injection period tables will be presented for the FAS as well.

An overall summary of –AEs will be presented, which includes:

- a. the number and percentage of subjects experiencing an AE in pre-injection period
- b. the number and percentage of subjects experiencing a TEAE during the acute first injection, inter-injection, acute second injection, post-second injection, and post-injection periods
- c. the number and percentage of subjects experiencing an AE by greatest intensity in pre-injection period
- d. the number and percentage of subjects experiencing a TEAE by greatest intensity during the acute first injection, inter-injection, acute second injection, post-second injection, and post-injection periods
- e. the number and percentage of subjects experiencing an AE related to biopsy during the pre-injection period
- f. the number and percentage of subjects experiencing a TEAE related to biopsy during the acute first injection, inter-injection, acute second injection, post-second injection, and post-injection periods
- g. the number and percentage of subjects experiencing a TEAE related to REACT investigational product during the acute first injection, inter-injection, acute second injection, post-second injection, and post-injection periods
- h. the number and percentage of subjects experiencing a TEAE related to REACT injection procedure during the acute first injection, inter-injection, acute second injection, post-second injection, and post-injection periods
- i. the number and percentage of subjects experiencing an SAE during the pre-injection period

- j. the number and percentage of subjects experiencing a treatment emergent SAE (TESAE) during the acute first injection, inter-injection, acute second injection, post-second injection, and post-injection periods
- k. the number and percentage of subjects experiencing a TEAE leading to study discontinuation during the acute first injection, inter-injection, acute second injection, post-second injection, and post-injection periods
- l. the number and percentage of subjects experiencing a TEAE leading to death during the acute first injection, inter-injection, acute second injection, post-second injection, and post-injection periods

In the overall summary of AEs table, besides tabulating the number and percentage of subjects, the total number of AE episodes will also be provided. If a subject has repeated episodes of a particular AE, all episodes will be counted in the summary table.

Additionally, each of the categories of events presented in the overall summary of AEs table will be summarized by SOC and PT in individual tables. In the remaining summary tables, the incidence of TEAEs will be calculated by dividing the number of subjects who have experienced the event by the total number of subjects in the analysis set. Thus, the incidence of TEAEs is shown in terms of the total number of subjects and not in terms of the total number of episodes. If a subject has repeated episodes of a particular TEAE, only the most severe episode, or the episode with the strongest causal relationship to biopsy, REACT product, or REACT injection procedure will be counted in the summary tables.

A subject with more than one type of TEAE in a particular SOC will be counted only once in the total number of subjects experiencing TEAEs in that particular SOC. Since a subject could have more than one type of TEAE within a particular SOC, the sum of subjects experiencing different TEAEs within the same SOC could appear greater than the total number of subjects experiencing TEAEs in that SOC. Similarly, a subject who has experienced a TEAE in more than one SOC will be counted only once in the total number of subjects experiencing AEs in those SOCs.

All AEs will be presented in tables in descending order from the SOC with the highest incidence to the SOC with the lowest incidence. Within each SOC, AEs will be sorted in descending order from the PT with the highest incidence to the PT with the lowest incidence.

The occurrences of all AEs will be listed for each subject. Individual listings of each of the categories of AEs described above will also be presented (e.g., TEAEs leading to study discontinuation). Listings will contain all collected information using the FAS. Listings will be sorted by subject identification number, onset date, SOC, and PT. If the onset date is completely missing, then these events will be presented first. If the onset date is missing a month or a day, then these events will be presented before any complete dates. The listing will display the dates as they are collected. That is, if imputed dates were used to determine if the AE is treatment emergent, the imputed dates will not be displayed in the listing.

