#### 6.5. Follow-up Visits

The subject will return to the clinic for follow-up visits on Days 1 (if discharged day of REACT injection), 7, 14, and 28 ( $\pm$  3 days) and Months 2, 3, 4 and 5 ( $\pm$  7 days) after the first REACT injection, and on Days 1 (if discharged day of REACT injection), 7, 14, and 28 ( $\pm$  3 days) and Months 2 and 3 ( $\pm$  7 days) after the second REACT injection ([Table 1](#) and [Table 2](#)). The subject will also report to the clinical center 10 to 14 days before the planned, final REACT injection to undergo pre-treatment assessments. **Every attempt should be made to ensure that the second REACT injection is administered 6 months after the first injection.**

Following the final REACT injection, subjects will complete long-term, follow-up assessments of safety and efficacy through Months 6, 9, 12, 15, 18, 21, and 24 ( $\pm$  7 days) post-treatment.

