3. INVESTIGATIONAL PLAN

3.1 Study Design

This is a multi-center, prospective, open-label, single-group study. Up to 10 subjects who complete screening procedures and satisfy all inclusion and exclusion criteria specified in the protocol will be enrolled into the study immediately prior to the biopsy. All subjects will be treated with two REACT injections 6 months (+4 weeks) apart after biopsy. Subjects will be followed over a 24 month period post the last injection. See Appendices A-B for the Schedule of Events.

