4.9 Analysis Periods

The following analysis periods will be defined as:

- Pre-Injection Period: from the start day of biopsy to the first REACT injection.
- Acute First Injection Period: from the first REACT injection to 1 month following the first REACT injection. The acute first injection period is a subset of the inter-injection period defined below.
- Inter-Injection Period: from the first REACT injection to either the second REACT injection or (if no such second injection was delivered) trial withdrawal or completion.
- Acute Second Injection Period: from the second REACT injection to 1 month following the second REACT injection. The acute second injection period is a subset of the post-second-injection period defined below.
- Post-Second Injection Period: from the second REACT injection to trial withdrawal or completion. This period will not apply to participants for whom only one REACT injection was delivered.
- Post-Injection Period: from the first REACT injection to trial withdrawal or completion. This period includes both the inter-injection and post-second injection periods.

[figure not shown]
If necessary, imputed dates will be used to determine the analysis period for adverse events.

Figure 1. Analysis Period Diagram for Subjects that Received Two Injections

Abbreviations: EOS = End of Study

Figure 2. Analysis Period Diagram for Subjects that Received One Injection

Abbreviations: EOS = End of Study

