7.3 Clinical Laboratory Assessments

Measurement of clinical laboratory parameters will be conducted at the time points presented in the [Appendix B](#). For purposes of analyses, laboratory results based upon standardized units will be used.

Results from all clinical laboratory parameters including pregnancy test will be presented in data

listings for the FAS.

For the IAS, a summary of the laboratory parameters at baseline, each scheduled post-baseline visit and change from baseline will be provided by test category (e.g., chemistry, hematology, etc.). Continuous clinical laboratory values will be summarized by presenting descriptive statistics. UACR will be considered as a categorical variable with three categories: <30 mg/g, 30 – 299 mg/g, and \geq 300mg/g. Qualitative results at each time point measured will be summarized by presenting the number and percentage of subjects.

Laboratory assessment results from unscheduled visits will be excluded from table summaries but will be included in data listings. When there are repeat measurements for a given visit (i.e. retests), only the last measurement will be listed and used in the table summaries.

Results that are reported as above or below the limit of quantitation (e.g. <4, >10) will be not be imputed and will be treated as missing values for summarization purposes. The originally reported result (e.g. <4, >10) will be displayed in the listings.

Laboratory abnormalities will be defined using the NCI CTCAE grading scheme. Abnormal laboratory values will be flagged as above or below the normal range.

For the IAS, the incidence of treatment-emergent laboratory abnormalities, defined as values that increase at least one toxicity grade between baseline and post-baseline up to six months following REACT injection, will be summarized. If baseline and pre-injection data are missing, then any graded abnormality (i.e., at least a Grade 1) will be considered as treatment-emergent. These values will be summarized descriptively for the IAS.

Additionally, for the IAS, shift tables (shift from baseline to the worst post-baseline value) will be presented split by the inter-injection, post-second injection period, and the post-injection period as described in [section 4.9](#). Shift tables will describe the shift in CTCAE grades when available, or the shift from low/normal/high when CTCAE grades are not available.

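### AE percentages and worst-value laboratory shifts are not comparable between the inter-injection and post-second-injection periods; a matched window after each injection is a cheap improvement.

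*SAP*

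**What the plan says.** - **Periods (SAP 4.9).** Two short periods have equal length: "Acute First Injection Period: from the first REACT injection to 1 month following the first REACT injection" and "Acute Second Injection Period: from the second REACT injection to 1 month following the second REACT injection". The inter-injection period starts at the first injection and runs "to either the second REACT injection or (if no such second injection was delivered) trial withdrawal or completion". The post-second period starts at the second injection, ends at withdrawal or completion, and does not apply to a subject with one injection. SAP 3.1 plans "two REACT injections 6 months (+4 weeks) apart after biopsy" and 24 months of follow-up after the last one.
- **Adverse events (SAP 7.2.5).** The overall summary gives "the number and percentage of subjects experiencing a TEAE during the acute first injection, inter-injection, acute second injection, post-second injection, and post-injection periods". The same five periods are used for intensity, relatedness, seriousness, discontinuation and death, and total episode counts are added. The SOC and PT tables divide by the number of subjects in the analysis set. No other denominator is named for the overall table, and no patient-time is specified.
- **Laboratory values (SAP 7.3).** For the IAS, "shift tables (shift from baseline to the worst post-baseline value) will be presented split by the inter-injection, post-second injection period" and the whole post-injection period. The acute periods are not used here. Unscheduled results are left out of the table summaries.
- **Visits (Protocol 6.5).** Days 1 (if discharged on the injection day), 7, 14 and 28 and Months 2 and 3 are common to both injections. The first injection also has Months 4 and 5. For the second, "Following the final REACT injection, subjects will complete long-term, follow-up assessments of safety and efficacy through Months 6, 9, 12, 15, 18, 21, and 24".
- **Status (SAP 9).** The analysis is mainly descriptive, without hypothesis tests.

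**The concern.** The SAP splits its safety tables by injection, so a reader will set the inter-injection column beside the post-second column and ask whether safety changed after the second injection. Three things other than risk differ between those columns: the length of observation, the spacing of visits, and who contributes. A subject with one injection adds up to 24 months to the inter-injection column and nothing to the post-second column, yet would remain in the denominator of both if the analysis set is used.

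Product- and procedure-related events, the primary endpoint in SAP 2.2.1, are shown by these same periods. For laboratory shifts, more time and more draws in a progressive disease give more chances of a poor worst value. At stake is a false impression of cumulative harm or, where second injections are withheld, a false impression of none.

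**Working it through.** **Inputs.** Injection interval 6 months, up to 4 weeks more (SAP 3.1); follow-up 24 months after the last injection (SAP 3.1); visits from Protocol 6.5; up to 10 subjects (SAP 9). Event rates and per-draw probabilities are not in the documents and are assumed over a range. Full follow-up is assumed throughout.

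**1. The plan's own figure.** Protocol 4.5 states 31 months: 1 + 6 + 24 = 31. It reproduces. With the full 4-week window (28/30.4375 = 0.92 month) the inter-injection period is 6.92 months and the total 31.92.

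**2. Visit density.** After the first injection there are 8 follow-up visits: 8/6 = 1.33 per month, or 8/6.92 = 1.16. The pre-injection visit and the optional Month 6 visit would raise this. After the second there are 4 + 2 + 7 = 13 visits: 13/24 = 0.54 per month, and 7/21 = 0.33 per month after Month 3. In the first month both schedules have the same 4 visits.

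**3. Background events, unchanged rate, all subjects injected twice.** P(t) = 1 − exp(−rate × t).

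| Assumed rate per month | 6 months | 24 months | Ratio |
|---|---|---|---|
| 0.01 | 5.8% | 21.3% | 3.7 |
| 0.02 | 11.3% | 38.1% | 3.4 |
| 0.05 | 25.9% | 69.9% | 2.7 |
| 0.10 | 45.1% | 90.9% | 2.0 |

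**4. Some subjects receive only one injection.** Take 10 subjects, a rate of 0.05 and the analysis set as denominator, with n2 subjects injected twice. Inter-injection = [n2 × P(6) + (10 − n2) × P(24)]/10. Post-second = n2 × P(24)/10. Acute second = n2 × P(1)/10.

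| n2 | Inter-injection | Post-second | Acute first | Acute second | Patient-months, inter / post-second |
|---|---|---|---|---|---|
| 10 | 25.9% | 69.9% | 4.9% | 4.9% | 60 / 240 |
| 8 | 34.7% | 55.9% | 4.9% | 3.9% | 96 / 192 |
| 6 | 43.5% | 41.9% | 4.9% | 2.9% | 132 / 144 |

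With n2 = 6: (6 × 0.2592 + 4 × 0.6988)/10 = 0.435, against 6 × 0.6988/10 = 0.419. The order reverses with no change in risk. If only subjects who received the second injection are counted, post-second is 69.9% and acute second 4.9% in every row.

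**5. Worst-value shifts.** P(at least one) = 1 − (1 − p)^k. Protocol Table 2 is broken in the available text; read from its visit columns, which show no Day 7, there are 7 to 9 draws between injections and 12 after the second. At p = 0.05 per draw this gives 30% to 37% against 46%; at 0.02, 13% to 17% against 22%; at 0.10, 52% to 61% against 72%. Independent draws are assumed, which overstates the effect for correlated results.

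**6. Events clustered after injection.** If 30% of subjects have an event in the first month after each injection and none later, both columns show 30%. Whole-period rates then mislead: 3 events after each injection give 3/60 = 5.0 against 3/240 = 1.25 per 100 patient-months, although the risk per injection is the same.

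**The case against.** The strongest reply is that the SAP already contains a like-for-like comparison. The two acute periods each last 1 month, share the same visits, and are used for every TEAE category. The procedure-related events that Protocol 8.1.1.3 describes, such as pain and hemorrhage, follow the biopsy or injection, so for them the acute columns are the relevant ones and period length matters little. This stands. It leaves out later AEs, and the laboratory shift tables have no acute columns.

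For laboratory values, SAP 7.3 also summarises each scheduled visit and limits treatment-emergent abnormalities to six months after injection. That helps, but the text does not say which injection starts the six months, and by-visit means do not replace a matched worst-value shift.

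It is also fair to say that the period boundaries are defined and diagrammed, that AE onset dates and injection data are listed, and that with up to 10 subjects a reader could derive rates. Late under-detection of AEs cannot be shown from visit spacing alone, because Protocol 8.1.1 requires all AEs to be recorded through 24 months and allows unscheduled visits. These points limit the weight of the concern. They do not make the two columns comparable.

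A reader might infer that the post-second column must always be the larger. The documents do not support that: step 4 shows a reversal, SAP 3.2.4 foresees withheld second injections, and step 6 shows equal columns for clustered events.

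**Conclusion.** The point holds as a cheap improvement. The inter-injection and post-second columns differ in length, visit spacing and subjects at risk. For background events at an unchanged rate, the post-second percentage is expected to be about 2.0 to 3.7 times the inter-injection percentage over assumed rates of 0.01 to 0.10 per month, provided all subjects receive both injections and complete follow-up. If several do not, the gap narrows and can reverse. The effect on worst-value shifts is smaller, for example 30% to 37% against 46% at an assumed 5% per draw.

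The result rests on a constant background rate and on the analysis set as denominator. It does not describe events clustered just after an injection. It would also be too strong to infer that no matched comparison exists, since the acute periods provide one for early AEs. That pair, too, is diluted if the second-injection column is divided by the whole IAS (4.9% against 3.9% with 8 of 10). No test or decision rule depends on these tables, so the consequence is for interpretation only.

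**What to change.** 1. Keep the existing percentages in SAP 7.2.5 and the existing shift tables in SAP 7.3.
2. Add one equal-length comparison after each injection. For AEs, use the first 6 months after the first injection and the first 6 months after the second. For worst-value shifts, use only scheduled visits common to both schedules, which match through Month 3.
3. In that comparison, take as denominator the subjects who received the injection in question.
4. For each SAP 4.9 period, show the number of subjects entering and the patient-months. Events per patient-year may be added as a supplement, with a note that rates over unequal periods dilute events clustered after injection. They should not be the main comparison.

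The cost is one extra table and a few columns from data already collected. Estimates from up to 10 subjects will be imprecise. Visit spacing still differs after Month 3, so the 6-month AE window is matched in length but not fully in contacts. Because SAP 4.7 fixes baseline before the first injection, shifts in the second window will still include any progression between injections; a footnote should say so.

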## 5. STUDY POPULATION

### 5.1. Subject Inclusion Criteria

Unless otherwise noted, subjects must satisfy each inclusion criterion to participate in the study. Inclusion criteria will be assessed at the Screening Visit, prior to renal biopsy, and before each REACT injection unless otherwise specified.

1. The subject is male or female, 30 to 65 years of age on the date of informed consent.
2. The subject has an established diagnosis of T2DM.
3. The subject has an established diagnosis of diabetic nephropathy as the underlying cause of renal disease.
4. The subject has an established diagnosis of CKD not requiring renal dialysis, defined as having an eGFR between 14 and 20 mL/min/1.73m^2 inclusive at the Screening Visit and prior to REACT injection.
5. The subject has blood pressure less than 150/90 at the Screening Visit, prior to renal biopsy, and prior to REACT injection(s). At the time of the biopsy and injections, the subject's BP should not be significantly below the previously recorded stable pressure.
6. The subject has stable blood pressure and is maintained on a stable anti-hypertensive medication regimen, if treatment for hypertension is necessary. If treatment includes an angiotensin-converting-enzyme inhibitor (ACEI) or an angiotensin receptor blocker (ARB), that treatment must have been initiated at least 8 weeks prior to renal biopsy. Treatment must be stable during the 6-week period immediately prior to REACT injection. Stable treatment is defined as dose adjustment to no less than one half of the current dosage or to no more than 2 times the current dosage. Dose interruptions up to 7 days due to medical necessity are allowed.
7. A minimum of 3 measurements of eGFR or sCr should be obtained at least 3 months apart prior to the Screening Visit or within the previous 24 months to define the rate of progression of CKD. The subject should have adequate, historical clinical data to provide a reasonable estimate of the rate of progression of CKD. The Medical Monitor may be consulted to ensure there is sufficient data.
8. The subject is willing and able to refrain from NSAID consumption (including aspirin) as well as clopidogrel, prasugrel, or other platelet inhibitors during the period beginning 7 days before through 7 days after both the renal biopsy and REACT injection(s).

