3.2.4 Treatment Compliance

Eligible subjects will receive their autologous REACT preparations via a series of up to two injections. The investigational product will be administered into the biopsied kidney using a percutaneous approach. REACT product preparation and dosing procedures are specified in this protocol as well as the Study Reference Manual.

It is anticipated that all subjects will receive two REACT injections. In some cases, a subject or the Investigator may elect to delay or withhold the second REACT injection. For example, if there appears to be any untoward safety risk, or if the subject's health status would, in the judgment of the Investigator, be jeopardized, then the second REACT injection should not be administered.

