4.2 Analysis Sets

The following analysis sets will be used in the statistical analyses.

Full Analysis Set (FAS): The FAS will consist of all subjects who are enrolled in the study. Subjects are considered enrolled once biopsy is taken.

Injection Analysis Set (IAS): The IAS will include all subjects who receive at least one REACT injection.

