5. STUDY SUBJECTS

5.1 Disposition of Subjects

Subject disposition including number of subjects screened, frequency count and proportion of screen failures will be summarized for all screened subjects. Additionally, a summary of enrolled/biopsied, received one or two REACT injections, stage of withdrawal and reason, completed study will be summarized for all screened subjects by presenting frequency counts and the proportion of subjects. A by subject listing of all screened subjects will also be provided.

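### Two SAP adverse-event rules can misstate the tables: second-injection incidence is divided by everyone injected, and a missing intensity is tabulated as Grade 5 (death)

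*SAP*

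**What the plan says.** **Denominator.** SAP 7.2.5 presents treatment-emergent AE (TEAE) summaries for the IAS, and SAP 4.2 defines that set: "The IAS will include all subjects who receive at least one REACT injection". In the tables by system organ class and preferred term, incidence is "calculated by dividing the number of subjects who have experienced the event by the total number of subjects in the analysis set". Those tables cover every category of the overall summary, and each TEAE row there includes the acute second injection period and the post-second injection period. The overall summary gives percentages for the same periods without stating a denominator.

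SAP 4.9 says of the post-second injection period: "This period will not apply to participants for whom only one REACT injection was delivered". It adds: "The acute second injection period is a subset of the post-second-injection period defined below". Neither period therefore exists for a subject injected once.

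The plan foresees such subjects. SAP 3.2.4 says "a subject or the Investigator may elect to delay or withhold the second REACT injection", and the disposition summary in SAP 5.1 counts those who "received one or two REACT injections".

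**Missing intensity.** SAP 7.2.2 treats an AE with no recorded intensity as Grade 5, and its own scale defines Grade 5 as death. SAP 4.5 says that missing data are not imputed. In SAP 7.2.5, rows c and d tabulate subjects by greatest intensity, and row l separately tabulates TEAEs leading to death.

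**Grade changes.** Protocol 8.2.1 has a change of grade over a longer period recorded as a separate event with its own dates. SAP 7.2.1 counts as treatment-emergent any AE that begins after the first injection, or an earlier one that worsens in severity or frequency after it.

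**The concern.** Procedure- and product-related AEs are the primary endpoint, and these tables break them down by injection period. A reader will take the second-injection columns as the experience of subjects who had a second injection. If some injected subjects did not, the percentage is diluted, and always downwards.

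The Grade 5 rule is a different kind of error. Death is a known outcome, not a degree of severity that can be assumed as a cautious worst case. The rule can put a fatal-grade event in a table for a trial in which nobody died. Because the rows show each subject's greatest intensity, one ungraded record overrides every grade the investigator did record for that subject in that period.

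A secondary gap concerns grade changes. An AE that began before injection and improves afterwards generates a new record with a post-injection onset. Read literally, that record is treatment-emergent, although the worsening condition in SAP 7.2.1 suggests this is not intended. The SAP has no rule linking such records.

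**Working it through.** The plan states no incidence figure to reproduce. The check is of what each rule yields.

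**1. Second-injection denominator**

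Inputs: n = subjects in the IAS, taken as 10, the maximum in SAP 9; k = subjects given the second injection, not in the documents and varied here; x = subjects with an event in the period, also varied.

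- Printed under SAP 7.2.5: x/n
- Among subjects exposed in the period: x/k
- Ratio of printed to exposed: (x/n)/(x/k) = k/n

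| x | Printed (x/10) | k = 10 | k = 9 | k = 8 | k = 7 |
|---|---|---|---|---|---|
| 0 | 0% | 0% | 0% | 0% | 0% |
| 1 | 10.0% | 10.0% | 11.1% | 12.5% | 14.3% |
| 2 | 20.0% | 20.0% | 22.2% | 25.0% | 28.6% |
| 3 | 30.0% | 30.0% | 33.3% | 37.5% | 42.9% |

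For x = 3 the shortfall is 3.3, 7.5 or 12.9 percentage points at k = 9, 8 or 7. For x = 1 and k = 9 it is 1.1 points.

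**2. Can k be less than n?**

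SAP 3.2.4, 4.9 and 5.1 all provide for one-injection subjects, but no rate is given. If each subject independently has probability q of not being re-injected (an assumption), the chance that at least one of ten is not is 1 − (1 − q)^10:

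- q = 5%: 40%
- q = 10%: 65%
- q = 20%: 89%
- q = 30%: 97%

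Eligibility is one possible route. Protocol 5.1 has inclusion criteria checked "prior to renal biopsy, and before each REACT injection unless otherwise specified", and criterion 4 requires eGFR of 14 to 20 "inclusive at the Screening Visit and prior to REACT injection". If that window is applied again before the second injection, a subject assumed to be at 15 at the first injection falls below it after losing more than 1 unit in six months (1/0.5 = 2 units per year). From an assumed 16, the loss is more than 2 units (2/0.5 = 4 per year).

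**3. Missing intensity**

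One subject with one ungraded, non-fatal AE, n = 10:

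- SAP 7.2.2 rule: 1/10 = 10% at Grade 5
- Missing kept as missing: 0/10 = 0% at Grade 5

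If that AE is treatment-emergent, row d shows a Grade 5 subject while row l can show no TEAE leading to death, so the same table would disagree with itself. Row l covers only the periods from the first injection onwards, so a pre-injection AE in row c has no matching death row.

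**4. What is not affected**

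The post-injection, inter-injection and acute first injection periods apply to every IAS subject, so the denominator is right there. The relatedness rows (e to h) do not use intensity, so an ungraded AE changes none of their counts.

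**The case against.** The strongest reply is that neither rule changes the full-period primary endpoint. That is correct: the post-injection column uses the right denominator, and relatedness does not depend on intensity. The errors are confined to the second-injection breakdowns and the greatest-intensity rows.

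On the denominator, events over all injected subjects is a legitimate proportion, and the SAP does not call it an at-risk rate. The SAP's next sentence shows that the rule was written to separate subjects from episodes, and SAP 4.9 could be read as removing one-injection subjects from the period. All the same, the SAP states one denominator and gives no period-specific one. Its reason for using the IAS, that everyone in it has been treated, holds for the first injection but not necessarily for the second. Counts and disposition would let a reader recompute the figure, but that does not correct the printed one.

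The plan expects two injections for everyone, in which case the error is zero. The eGFR illustration is also open to challenge: criterion 4 refers to injection in the singular, so whether the window applies again is arguable. The point does not depend on it, because the SAP itself allows for one-injection subjects.

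On missing intensity, Protocol 8.3 requires intensity for each reportable event, and SAP 4.1 has queries resolved before lock, so the rule will probably never operate. Row l and the listings would also help a reader spot a false Grade 5. These points limit the consequence; they do not justify the rule. The comparison with treating a missing relationship as related is weak, because relatedness is a judgement and death is a fact.

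On grade records, the organ-class and preferred-term tables already count a subject once per event. That settles repeat episodes, but not whether an improving pre-injection AE makes the subject a TEAE case at all.

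**Conclusion.** The concern holds on both main parts, and both should be fixed.

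- **Denominator:** the printed second-injection percentage is k/n of the percentage among exposed subjects. It is wrong as a rate in those subjects only if at least one injected subject is not re-injected and at least one event occurs. The direction is always understatement.
- **Missing intensity:** each affected subject adds 1/n to the Grade 5 row, or 10% at n = 10. There is no effect if every intensity is complete at lock, which is likely.

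The values of k, x and q are assumptions. The overall impact is limited: there are at most ten subjects, no hypothesis test is planned, and full listings are provided. Neither the sample size nor the full-period primary result changes. The grade-record gap is secondary, and the conclusion does not rest on it.

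**What to change.** 1. **SAP 7.2.5.** For the acute second and post-second injection periods, in the overall table and in every organ-class and preferred-term table, divide by the IAS subjects who received the second injection. Print that N in the column header.
2. **SAP 7.2.2.** Delete the Grade 5 rule. Show missing intensity as its own category, and reserve Grade 5 for events the investigator graded 5 or reported under the fatal-outcome criterion in SAP 7.2.4. This also removes the conflict with SAP 4.5.
3. **SAP 7.2.1 (secondary).** State that a post-injection record continuing a pre-injection AE is treatment-emergent only if its grade or frequency exceeds the pre-injection level. Count linked grade records as one episode.

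The cost is SAP wording and table programming, with no new data collection. Item 3 also needs a linking rule or a data-management flag. If any subject is not re-injected, the second-period percentages will rest on a smaller N.
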